4. INVESTIGATIONAL PLAN

4.1 Overall Study Design

This is an open-label, multicenter, dose-escalation, safety and biomarker prediction study of alvocidib followed by 7+3 therapy in adults with newly diagnosed and previously untreated AML.

Induction – Alvocidib and 7+3

The starting dose of alvocidib will be 20 mg/m² as a 30-minute intravenous (IV) bolus followed by 30 mg/m² over 4 hours as an IV infusion administered daily on Days 1-3 of Induction. Patients will have a one day drug holiday (Day 4) before initiation of the 7+3 regimen. Beginning on Day 5, cytarabine will be administered as a 100 mg/m²/day continuous IV infusion for seven consecutive days (Days 5-11) plus daunorubicin administered at a dosage of 60 mg/m² via IV bolus of up to 15 minutes' duration on Days 5-7.

Escalation of the alvocidib dose will follow a standard 3+3 design with sequential cohorts of three patients treated with incrementally higher doses of alvocidib until a DLT is observed and the MTD is established. Three patients within a dose cohort may be enrolled without a waiting period between patients. Escalation to the next higher dose level will not occur until all patients within the current dose cohort have undergone full safety assessments (including count recovery or disease assessment).

If 1 of 3 patients in a cohort experiences a DLT, up to 3 additional patients will be treated at that dose level. If all patients in the expanded cohort have undergone full safety assessments (including count recovery or disease assessment) with no additional DLTs observed, the alvocidib dose will be escalated in a new cohort of 3 patients. If 2 or more of 3-6 patients at a given dose level experience a DLT during the first cycle, then the MTD will have been exceeded and up to a total of 6 patients will be treated at the previous lower dose level. If 0 or 1 of 6 patients experiences a DLT at this previous lower dose level, this dose will be declared the MTD.

The MTD is defined as the dose at which ≤1 of 6 patients experience a DLT during Cycle 1 with the next higher dose having at least 2 of 3-6 patients experiencing a DLT during Cycle 1.

The period of DLT determination for alvocidib and 7+3 ends at the start of consolidation therapy. However, any AEs that occur during Reinduction and meet DLT criteria will be taken into consideration when determining whether to escalate the dose of alvocidib and when defining the MTD.

Once the MTD has been established, up to 20 additional patients will be enrolled at the MTD level for confirmation of safety as well as additional safety analysis and feasibility for determining MRD by dual methods (ie, MPFC and NGS) at a central laboratory.

Disease Assessment

On Day 14 (± 3 days), unless medically contraindicated, peripheral blood and bone marrow samples will be collected for disease assessment including MRD.

Patients with **no** evidence of residual leukemia ($\leq 5\%$ bone marrow blasts plus $\leq 10\%$ cellularity) will be monitored weekly and will undergo response assessment at the time of hematologic recovery (ie, absolute neutrophil count (ANC) $> 1000/\mu\text{L}$ and platelet count $> 100,000/\mu\text{L}$) or Day 50 (± 3 days), counted from Day 1 of Induction therapy, whichever occurs first. At this time, the patient may continue to Consolidation therapy with HiDAC.

Reinduction – Alvocidib and 5+2

Patients **with** evidence of residual leukemia ($> 5\%$ bone marrow blasts plus $> 10\%$ cellularity) may be eligible for a second induction cycle (or 'Reinduction') with alvocidib and 5+2 at the discretion of the Investigator. The dose of alvocidib will remain the same, but the 7+3 regimen will be changed to 5+2: cytarabine, $100 \text{ mg}/\text{m}^2/\text{day}$, as a continuous IV infusion on Days 5-9 plus daunorubicin administered at a dosage of $45 \text{ mg}/\text{m}^2$ via IV bolus of up to 15 minutes' duration on Days 5 and 6.

Should a patient undergo Reinduction therapy, they will be monitored weekly and will undergo response assessment at the time of hematologic recovery (ie, ANC $> 1000/\mu\text{L}$ and platelet count $> 100,000/\mu\text{L}$) or Day 60 (± 3 days), counted from Day 1 of Induction therapy, whichever occurs first. Upon documented hematologic recovery, the patient may continue to Consolidation therapy with HiDAC. Additional bone marrow assessments may be obtained per investigator discretion.

Investigators are permitted to administer intrathecal (IT) chemotherapy per institutional protocols after Induction (preferably during marrow aplasia), but before starting Consolidation therapy. Additional doses of IT chemotherapy may be administered after discussion with the Medical Monitor.

During both Induction and Reinduction, if necessary, care must be taken to ensure the patient's lifetime daunorubicin equivalent does not exceed $460 \text{ mg}/\text{m}^2$ (see [Appendix G](#) for conversion table) or that their left ventricular ejection fraction (LVEF) does not drop below 45%.

No intra-patient escalation of the alvocidib dose is permitted.

Consolidation – HiDAC

Consolidation therapy with HiDAC may be initiated at the time of hematologic recovery or within 90 days of recovery. Consolidation therapy may start before complete hematologic recovery after discussion with the Medical Monitor. It is not anticipated that all patients will undergo Consolidation therapy.

The HiDAC regimen will consist of 3 gm/m² IV every 12 hours on Days 1, 3, and 5 (a reduced dosage of 1.5 gm/m² is permitted for patients aged 60 to 65 years) (ie, a total of 6 doses over the 3-day regimen). The starting dose of HiDAC may be decreased pending discussion between the investigator and Medical Monitor.

Patients who plan to receive chemotherapy-based consolidation should get a minimum of two cycles of Consolidation up to a maximum of four cycles. Patients proceeding to stem cell transplant for Consolidation should get one cycle of Consolidation, if possible, to ensure disease stability while transplant plans are being made.

4.2 Patient Population

Patients enrolled in this study must be newly diagnosed with previously untreated AML excluding those patients with acute promyelocytic leukemia (APL-M3) or core-binding factor AML (CBF-AML).

4.2.1 Number of Patients

A sufficient number of patients will be screened in order to obtain up to 40 eligible and evaluable patients for dosing. Any patient who withdraws from the study before completing Induction/Reinduction therapy will be replaced unless that patient is withdrawn due to toxicity or has experienced a DLT.

4.2.2 Inclusion Criteria

To be eligible for participation in the study, patients must meet all of the following inclusion criteria:

1. Be between the ages of ≥ 18 and ≤ 65 years
2. Have an established, pathologically confirmed diagnoses of AML by World Health Organization (WHO) criteria with $\geq 20\%$ bone marrow blasts based on histology or flow cytometry
3. Be newly diagnosed and previously untreated
4. Have an Eastern Cooperative Oncology Group (ECOG) performance status (PS) ≤ 2
5. Have a serum creatinine level ≤ 1.8 mg/dL
6. Have an alanine aminotransferase (ALT) and aspartate aminotransferase (AST) level ≤ 5 times upper limit of normal (ULN)

7. Have a total bilirubin level ≤ 2.0 mg/dL (unless secondary to Gilbert syndrome, hemolysis, or leukemia)
8. Have a left ventricular ejection fraction (LVEF) $>45\%$ by echocardiogram (ECHO) or multigated acquisition (MUGA) scan
9. Be nonfertile or agree to use an adequate method of contraception. Sexually active patients and their partners must use an effective method of contraception associated with a low failure rate prior to study entry, for the duration of study participation, and for at least 6 months after the last dose of study drug (see [Section 4.5.3](#)).
10. Be able to comply with the requirements of the entire study.
11. Provide written informed consent prior to any study related procedure. (In the event that the patient is re-screened for study participation or a protocol amendment alters the care of an ongoing patient, a new informed consent form must be signed.)

4.2.3 Exclusion Criteria

Patients meeting any one of these exclusion criteria will be prohibited from participating in this study.

1. Received any previous treatment for AML
2. Diagnosed with APL-M3 or CBF-AML
3. Require concomitant chemotherapy, radiation therapy, or immunotherapy. Hydroxyurea is allowed up to the evening before starting (but not within 12 hours) of starting Induction therapy.
4. Received >200 mg/m² equivalents of daunorubicin (see [Appendix G](#) for conversion table)
5. Have a peripheral blast count of $>30,000/\text{mm}^3$ (may use hydroxyurea as in #3 above)
6. Have active central nervous system (CNS) leukemia
7. Have evidence of uncontrolled disseminated intravascular coagulation
8. Have an active, uncontrolled infection
9. Have other life-threatening illness
10. Have other active malignancies or diagnosed with other malignancies within the last 6 months, except nonmelanoma skin cancer or cervical intraepithelial neoplasia
11. Have mental deficits and/or psychiatric history that may compromise the ability to give written informed consent or to comply with the study protocol.
12. Are pregnant and/or nursing

4.3 Study Treatments

4.3.1 Calculation of Dose

The dosage of study drugs will be recalculated at the beginning of each new treatment cycle to reflect changes in the body surface area (BSA) that may have occurred but will remain the same for all treatments within a treatment cycle.

4.3.2 Study Drug Administration

Induction – Alvocidib and 7+3

- *Days 1, 2, 3:* Alvocidib at a starting dose of 20 mg/m² as a 30-minute (±10 minutes) IV bolus followed by 30 mg/m² administered as a 4-hour (±15 minutes) IV infusion (this is the starting dose for Cohort 1; see [Table 3](#) for assigned alvocidib doses per treatment cohort)
- *Day 4:* Drug-free day
- *Days 5, 6, 7: (7+3)* Daunorubicin 60 mg/m² via IV bolus of up to 15 minutes' (±5 minutes) duration each day followed immediately by;
- *Days 5, 6, 7, 8, 9, 10, 11:* Cytarabine 100 mg/m²/day via continuous 24-hour IV infusion (±2 hours for infusion duration each day)

Reinduction – Alvocidib and 5+2

Patients **with** evidence of residual leukemia defined as >5% bone marrow blasts plus >10% cellularity, based on the Day 14 (±3 days) bone marrow will be eligible to start a second induction cycle (ie, Reinduction) with alvocidib plus 5+2. The second induction cycle with alvocidib plus 5+2 will be allowed per investigator discretion.

- *Days 1, 2, 3:* Alvocidib at same dosage as during Induction
- *Day 4:* Drug-free day
- *Days 5, 6: (5+2)* Daunorubicin 45 mg/m²/day via IV bolus of up to 15 minutes' (±5 minutes) duration each day followed immediately by;
- *Days 5, 6, 7, 8, 9:* Cytarabine 100 mg/m²/day via continuous IV infusion (±2 hours for infusion duration each day)

Consolidation – HiDAC

Consolidation therapy will consist of high-dose cytarabine (HiDAC) which may be initiated at the time of hematologic recovery or within 90 days of recovery. Consolidation therapy may start before complete hematologic recovery after discussion with the Medical Monitor. It is not anticipated that all patients will undergo Consolidation therapy.

- *Days 1, 3, 5:* HiDAC 3 gm/m² IV every 12 hours (1.5 gm/m² in patients aged 60 to 65 years) (ie, a total of 6 doses over the 3-day regimen); lower starting dose may be permitted at the discretion of the Investigator and after discussion with the Medical Monitor

Patients who plan to receive chemotherapy-based consolidation should get a minimum of two cycles of Consolidation up to a maximum of four cycles. Patients proceeding to stem cell transplant for Consolidation should get one cycle of Consolidation, if possible, to ensure disease stability while transplant plans are being made.

4.3.3 Dose Escalation of Alvocidib

Evaluation of the safety and efficacy of alvocidib and 7+3 in patients with newly diagnosed AML will occur in two steps:

- Step 1: Cohorts of 3-6 patients will receive escalating doses of alvocidib based on Table 3 until a DLT is observed during Induction/Reinduction.
- Step 2: Confirmation of the MTD. Once the MTD has been established, up to 20 additional patients will be enrolled at the MTD level for confirmation of safety as well as additional safety analysis and feasibility for determining MRD by dual methods (ie, MPFC and NGS) at a central laboratory.

Table 3: Dose Escalation of Alvocidib

Dose Levels ^a	Alvocidib Dosing		Number of Patients
	IV Bolus	Continuous IV × 4 hrs	
Cohort -1 ^b	10 mg/m ²	15 mg/m ²	3-6
Cohort 1^c	20 mg/m²	30 mg/m²	3-6
Cohort 2	30 mg/m ²	40 mg/m ²	3-6
Cohort 3	30 mg/m ²	50 mg/m ²	3-6
Cohort 4	30 mg/m ²	60 mg/m ²	3-6

- a It is possible for additional and/or intermediate dose levels to be added during the cycle of the study.
- b Dose level -1 represents treatment doses for patients requiring a dose reduction from the starting dose level. It will also serve as a lower dose level if ≥2 patients at the starting dose level experience a DLT.
- c Starting Dose Level for first cohort of patients.

4.3.3.1 Dose Escalation of Alvocidib – Step 1

Escalation of the alvocidib dose will follow a 3+3 design. Sequential cohorts of three patients will be treated with escalated doses until the MTD is established. In the absence of DLTs, the dose will be increased incrementally. Three patients within a dose cohort may be enrolled without a waiting period between patients. Escalation to the next higher dose level will not occur until all patients within the current dose cohort have undergone full safety assessments (including count recovery or disease assessment).

If 1 of 3 patients in a cohort experiences a DLT, up to 3 additional patients will be treated at that dose level. If all patients in the expanded cohort have undergone full safety assessments (including count recovery or disease assessment) with no additional DLTs observed, the alvocidib dose will be escalated in a new cohort of 3 patients. If 2 or more of 3-6 patients at a given dose level experience a DLT during the first cycle, then the MTD will have been exceeded and up to a total of 6 patients will be treated at the previous lower dose level. If 0 or 1 of 6 patients experiences a DLT at this previous lower dose level, this dose will be declared the MTD.

4.3.3.2 Identifying and Confirming the MTD – Step 2

The MTD is defined as the dose at which ≤ 1 of 6 patients experience a DLT during Cycle 1 with the next higher dose having at least 2 of 3-6 patients experiencing a DLT during Cycle 1.

Any AEs that occur during Reinduction and meet DLT criteria will be taken into consideration when determining whether to escalate the dose of alvocidib and when defining the MTD.

Once the MTD has been established, up to 20 additional patients will be enrolled at the MTD level for confirmation of safety as well as additional safety analysis and feasibility for determining MRD by dual methods (ie, MPFC and NGS) at a central laboratory.

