	
possibly related to study drug and defined as follows based on the NCI CTCAE version 4.03:
 
• Any Grade 4 nonhematologic toxicity considered at least possibly drug related• Any Grade 3 nonhematologic toxicity considered at least possibly drug related and that does not resolve to \leqGrade 2 within 48 hours, with the following exceptions:
○ Grade 3 diarrhea, mucositis, nausea or vomiting will be considered dose-limiting only if resolution to \leqGrade 2 (including use of supportive care) requires more than 7 days• Grade 4 cytopenias lasting \geq50 days from the start of the cycle in the absence of residual leukemia if subject received one cycle of induction• Grade 4 cytopenias lasting \geq60 days in the absence of residual leukemia if subject received 2 cycles of induction• Grade 3 or 4 tumor lysis syndrome or related electrolyte disturbances (eg, hyperkalemia, hypophosphatemia, hyperuricemia) that do not resolve to \leqGrade 2 within 14 days• \geqGrade 3 elevations in creatinine that do not resolve to \leqGrade 2 within 7 days• Any AST and ALT elevation \geq5 \timesULN accompanied by serum bilirubin levels $>$2 \timesULN, regardless of duration• Any Grade 5 toxicity that is not clearly and incontrovertibly related to the underlying disease or extraneous causes• Anorexia, alopecia, fever, neutropenic fever, and infections of any grade should not be designated as DLTs since they are known and expected toxicities associated with the study drugs. 
If 1 of 3 patients in a cohort experiences a DLT, up to 3 additional patients will be treated at that dose level. If all patients in the expanded cohort have undergone full safety assessments (including count recovery or disease assessment) with no additional DLTs observed, the alvocidib dose will be escalated in a new cohort of 3 patients. If 2 or more of 3-6 patients at a given dose level experience a DLT during the first cycle, then the MTD will have been exceeded and up to a total of 6 patients will be treated at the previous lower dose level. If 0 or 1 of 6 patients experiences a DLT at this previous lower dose level, this dose will be declared the MTD.
 
The MTD is defined as the dose at which \leq1 of 6 patients experience a DLT during Cycle 1 with the next higher dose having at least 2 of 3 to 6 patients experiencing a DLT during Cycle 1.
 
Any AEs that occur during Reinduction and meet DLT criteria will be taken into consideration when determining whether to escalate the dose of alvocidib and when defining the MTD.
 
Once the MTD has been established, up to 20 additional patients will be enrolled at the MTD level for confirmation of safety as well as additional

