11.3 Data Analyses

The MTD is defined as the largest dose for which fewer than 33% of patients experience a DLT. The MTD will be estimated by the highest alvocidib dose for which the empirical incidence of DLT during Cycle 1 was less than 33% in combination with 7+3.

Incidence rates of treatment-emergent adverse events will be summarized within treatment group at the MedDRA preferred term and primary system organ class levels. Similar summaries will be made for subsets of AEs such as (1) those judged by the Investigator to be related to study treatment, and (2) serious adverse events (SAEs).

Other routine safety assessments (eg, clinical laboratory parameters and vital signs) will be summarized by standard deviation, median, minimum and maximum observed values and changes from baseline values.

The multivariate analysis and risk score prediction model by Montesinos and colleagues [38] will be used to assess the potential for development of TLS (see [Appendix F](#)).

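### The protocol gives two conflicting MTD rules without saying which governs; they part if the top planned dose is tolerated and no level is added, or if DLTs occur in Reinduction

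*Protocol*

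**What the plan says.** **Conduct rule.** Protocol 4.3.3.2 asks for at most 1 of 6 patients with a DLT at the dose, "with the next higher dose having at least 2 of 3-6 patients experiencing a DLT during Cycle 1". Section 4.1 agrees, and so does the synopsis: "with the next higher dose having at least 2 of 3 to 6 patients experiencing a DLT during Cycle 1". The only declaration step, in 4.3.3.1, also follows an exceeded dose: "If 0 or 1 of 6 patients experiences a DLT at this previous lower dose level, this dose will be declared the MTD".

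**Dose range.** Step 1 in 4.3.3 reads: "Cohorts of 3-6 patients will receive escalating doses of alvocidib based on Table 3 until a DLT is observed during Induction/Reinduction". Table 3 stops at Cohort 4. Footnote a adds: "It is possible for additional and/or intermediate dose levels to be added during the cycle of the study". Section 4.3.3.1 says: "In the absence of DLTs, the dose will be increased incrementally".

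**Expansion.** Step 2 in 4.3.3: "Once the MTD has been established, up to 20 additional patients will be enrolled at the MTD level for confirmation of safety".

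**Analysis rule.** Protocol 11.3: "The MTD will be estimated by the highest alvocidib dose for which the empirical incidence of DLT during Cycle 1 was less than 33" percent. It sets no minimum number of patients and does not require a higher dose to have been exceeded.

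**DLT window.** Section 4.4.3 covers Induction and Reinduction, and 4.1 ends DLT determination when consolidation starts. Section 4.3.3.2 refers to Cycle 1 but then has DLT-type events in Reinduction weighed both for escalation and for the MTD. Section 11.3 refers to Cycle 1 alone.

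**SAP.** Section 4.2 lists defining the MTD as the first statistical objective, but the SAP gives no rule for it.

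**Size.** Protocol 11.2 anticipates up to 40 patients. It bases this on 3, 3, 6 and 3 patients at the four levels plus 20 more at the third.

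**The concern.** The MTD is part of the primary objective, and it fixes the dose for up to 20 further patients. When the conduct section and the analysis section can give different answers from the same data, the choice between them may be made after the data are seen.

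A tolerated top dose is foreseeable. Protocol Table 1 lists earlier studies of the hybrid schedule that gave 30/60 and 30/70 mg/m² with cytarabine and mitoxantrone, and 50/75 as monotherapy. The partner drugs differ, so this does not show that 30/60 is tolerable with 7+3. It does show that doses at or above this trial's ceiling had already been given. Yet the only scenario worked through in 11.2 is one in which Cohort 4 fails.

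**Working it through.** **1. Apply both rules to possible Cohort 4 results, with no level added above it.**

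| Cohort 4 DLTs | Incidence | Conduct rule (4.1, 4.3.3.2) | Section 11.3 |
|---|---|---|---|
| 0/3 | 0% | cleared; no MTD named | Cohort 4 |
| 0/6 or 1/6 | 0% or 16.7% | cleared; no MTD named | Cohort 4 |
| 2/6 | 33.3% | exceeded; go down one level | not Cohort 4 |

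On six patients the two rules draw the line in the same place (1/6 passes, 2/6 fails). They part on whether an exceeded higher dose is needed and on whether three patients are enough.

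**2. What 0 of 3 supports.** The one-sided 95% upper bound for 0 of n is 1 − 0.05^(1/n): 63% for 0/3 and 39% for 0/6. The exact (Clopper-Pearson) bound for 1/6 is 58%.

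**3. How often Cohort 4 is cleared.** The documents give no DLT rate for this combination, so the rates here are assumed. For a true rate p, a level is cleared with probability c(p) = (1−p)³ + 3p(1−p)²·(1−p)³. The values are c(5%) = 0.973, c(10%) = 0.906, c(15%) = 0.814, c(20%) = 0.709, c(30%) = 0.494 and c(40%) = 0.309. Multiply over the four levels:

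| Assumed DLT rates, Cohorts 1–4 | P(all four cleared) | Of these, Cohort 4 on 0/3 |
|---|---|---|
| 5% at each | 90% | 88% |
| 10% at each | 67% | 80% |
| 5/10/15/20% | 51% | 72% |
| 10/15/20/30% | 26% | 69% |
| 15/20/30/40% | 9% | 70% |

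The last column is (1−p)³ / c(p) at the Cohort 4 rate.

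**4. What six patients would add.** At a true Cohort 4 rate of 33%:
- Now: c(0.33) = 0.301 + 0.134 = 0.434.
- With six required: P(at most 1 of 6) = 0.67⁶ + 6(0.33)(0.67⁵) = 0.090 + 0.267 = 0.358.

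**5. DLT window.** Take six patients with one Induction DLT and one Reinduction DLT. If both count, as 4.1 and 4.3.3.2 allow, the result is 2/6 and the dose is exceeded. Under 11.3 it is 1/6 = 16.7% and the dose is kept. The protocol itself calls Reinduction a second induction cycle, and SAP section 3 ends Cycle 1 when cycle 2 study drug starts.

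**6. Sample size.** The scenario in 11.2 gives 3 + 3 + 6 + 3 + 20 = 35, so the stated 40 is not reproduced. Filling Cohort 4 to six gives 38. Filling all four levels gives 4 × 6 + 20 = 44. An allowance for replaced patients would reach 40 only at 12.5% (35 / 0.875 = 40), a rate stated nowhere.

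**The case against.** **A rule does exist.** A reader might infer that the protocol has no MTD rule, and no expansion dose at all, when the top dose is tolerated. The documents do not support that. Section 11.3 needs no exceeded dose and would name Cohort 4, and the expansion is tied to the MTD level. What remains is a conflict: the conduct sections are silent, the analysis section gives an answer, and nothing says which prevails. If 11.3 is meant only as a final-analysis estimate, it comes too late to choose the expansion dose.

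**The sponsor can keep escalating.** The text on increasing the dose in the absence of DLTs, together with footnote a, can be read as a cue to add a level once Cohort 4 clears. This stands in part. The gap needs two conditions, a cleared Cohort 4 and no added level. But footnote a permits a level without requiring one, and neither the next dose nor a ceiling is given.

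**Reinduction events are only weighed.** This stands. The conduct text leaves it to judgement how a Reinduction DLT counts, so the example in step 5 is a possible disagreement and not a certain one. No frequency is claimed for it. The SAP's Cycle 1 wording is also weak support, because its parenthesis concerns response classification and not DLTs.

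**Six patients is partly preference.** This largely stands. The bound for 1/6 (58%) is close to that for 0/3 (63%), and the expansion is itself meant to confirm safety.

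**The SAP sample table.** It shows 3, 3, 3 and 13 patients, with 13 at 30/60 and no higher level. A reader might infer that the gap did arise. The table is a template and may be illustrative, and it sets no rule.

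**The 40 is a ceiling.** The figure is hedged, withdrawals are replaced, and 35 lies below 40. This stands as to weight, but the derivation given still does not produce the figure.

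**Conclusion.** The protocol holds two MTD rules for one primary objective and ranks neither above the other. They diverge if Cohort 4 is tolerated and no level is added: the conduct rule then names nothing, while 11.3 names Cohort 4, possibly on three patients. They can also diverge at any level through Reinduction DLTs. This should be fixed.

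The clearance figures of 9% to 90% rest on assumed DLT rates and count Cycle 1 DLTs only. They are upper limits on how often the gap arises, because they ignore the option to add a level. The safety gain from six patients is modest: 36% against 43% clearance at a 33% DLT rate. The main gain is that the MTD and the expansion dose follow from one rule written in advance. The 35 against 40 discrepancy is minor; no inference depends on it.

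**What to change.** 1. Use one MTD rule and one DLT window, Induction plus Reinduction, in the synopsis, 4.1, 4.3.3.2 and 11.3.
2. Add a top-dose branch. If Cohort 4 has 0/3, treat three more patients there. If at most 1 of 6 has a DLT and no level is added, report *MTD not reached* and run the expansion at Cohort 4 as the highest tolerated dose. If 2 or more have a DLT, apply the existing de-escalation rule. A level added under footnote a becomes the top dose for this branch.
3. Remove the 33% estimator from 11.3, or give it the same six-patient minimum.
4. In 11.2 state 35 for the described scenario and 44 if all four levels are filled to six plus 20, or state the margin that explains 40. Align the synopsis and 4.2.1.

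**Cost.** Mostly wording. The three extra patients can come from the up-to-20, so the number treated at Cohort 4 need not rise (3 + 20 = 6 + 17 = 23). The real cost is their accrual time plus one further DLT assessment period before the expansion opens. That period ends at the start of consolidation, which may be up to 90 days after recovery, so it can run past Day 50 or 60.

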11.2 Sample Size

Given the design and primary objectives of this study, the sample size will be determined by the guidelines governing dose escalation/de-escalation and the identification of DLTs. As a result, the final sample size is not fixed and will not be determined by consideration of inferential analyses conducted via statistical hypothesis testing. It may be anticipated that the study sample size will be up to 40 patients. This is based on observing DLTs in 2 of 3 patients enrolled at the fourth dose level (Cohort 4) and declaring the third dose level as the MTD (3 patients each in the first and second dose levels, 6 patients in the third dose level during dose escalation, 3 patients at the fourth dose level, and an additional 20 patients at the third dose level for confirmation of safety as well as additional safety analysis and feasibility for determining MRD by dual methods [ie, MPFC and NGS] at a central laboratory). However, the actual number of patient enrolled may be slightly more or less depending on the actual pattern and frequency of DLTs.

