7.4. Interim Analysis

No interim analyses are planned. However, ongoing review of clinical data was performed during patient accrual and follow-up as required for dose escalation/de-escalation decisions.

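### The plan does not say whether DLTs in the MTD expansion count toward its under-33% MTD estimate, and gives no DLT check or consequence while up to 20 patients accrue

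*Protocol*

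**What the plan says.** Protocol Section 4.3.3 labels the expansion "Step 2: Confirmation of the MTD" and adds that "up to 20 additional patients will be enrolled at the MTD level for confirmation of safety", together with further safety analysis and the feasibility of measuring MRD by two methods.

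The MTD is characterised in two ways:

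- **By count.** Sections 4.1 and 4.3.3: "If 0 or 1 of 6 patients experiences a DLT at this previous lower dose level, this dose will be declared the MTD". The accompanying definition also requires at least 2 DLTs among 3 to 6 patients at the next higher dose. Every rule for escalating, or for judging that the MTD has been exceeded, is written for 3 to 6 patients.
- **By proportion.** Section 11.3: "The MTD is defined as the largest dose for which fewer than 33% of patients experience a DLT", with the estimator "The MTD will be estimated by the highest alvocidib dose for which the empirical incidence of DLT during Cycle 1 was less than 33" percent. It neither includes nor excludes expansion patients.

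On timing, Section 4.1 states: "The period of DLT determination for alvocidib and 7+3 ends at the start of consolidation therapy". This is not restricted to escalation patients.

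SAP Section 7.4 plans no interim analysis. It describes ongoing data review during accrual and follow-up "as required for dose escalation/de-escalation decisions". SAP Section 4.2 makes defining an MTD an objective, but the SAP has no DLT endpoint (Table 1), no DLT-evaluable population (Section 7.1) and no DLT table (Table 3).

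**The concern.** Finding the MTD and the DLTs is the primary objective. The expansion is the largest planned group at a single dose, and its stated role is confirmation. A confirmation step needs a statement of which data count, what result would fail to confirm, and what then happens. The plan supplies none of these for the expansion.

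Two things are at stake. Patients could continue to be enrolled at a dose whose observed DLT rate is above the protocol's own limit, with no written trigger for review. And the same final data could support opposite statements: MTD by the earlier 6-patient count, not MTD by the pooled proportion.

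**Working it through.** **Inputs.** Expansion of up to 20, and entry on 0 or 1 DLT in 6 (Protocol 4.3.3); limit of 33% (Protocol 11.3). The documents state no true DLT rate, so the rates p below are assumptions covering 20% to 50%.

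**The plan's own figure.** Protocol 11.2 says "It may be anticipated that the study sample size will be up to 40 patients". Its listed components give 3 + 3 + 6 + 3 + 20 = 35. The text does not explain the gap; a rounded ceiling or replacements could. It does not affect this point. No operating characteristic is stated for the expansion, so there is none to reproduce.

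**Step 1: evidence at entry.** The exact (Clopper-Pearson) 95% CI is 0.4% to 64% for 1/6, and has an upper limit of 46% for 0/6. The chance of at most 1 DLT in 6 is (1−p)^6 + 6p(1−p)^5:

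| True rate p | P(at most 1/6) | Expected DLTs in 20 (20p) |
|---|---|---|
| 20% | 66% | 4 |
| 33% | 36% | 6.6 |
| 40% | 23% | 8 |
| 50% | 11% | 10 |

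**Step 2: where the two definitions part.** Pooling 6 + 20 = 26 patients, 8/26 = 30.8% is under the limit and 9/26 = 34.6% (exact 95% CI 17% to 56%) is over it. A dose declared the MTD on 1/6 that then has 8/20 DLTs keeps that status under Section 4.3.3 and fails a pooled Section 11.3.

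**Step 3: what a pooled final check would detect.** Given at most 1/6, the prior count is 0 or 1 with weights proportional to (1−p)^6 and 6p(1−p)^5. Reaching 9/26 needs at least 9/20 after 0/6, or at least 8/20 after 1/6.

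- p = 40%: 0.20 × 0.404 + 0.80 × 0.584 = 0.55.
- p = 50%: 0.143 × 0.748 + 0.857 × 0.868 = 0.85.

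**Step 4: an example of checks during accrual.** Suppose the pooled proportion is compared with 33% after 5, 10 and 15 expansion patients. The smallest counts that meet the limit are 4/11 (36.4%), 6/16 (37.5%) and 7/21 (33.3%). The pause probability comes from exact enumeration: start from the Step 3 weights, add a Binomial(5, p) count at each look, and remove the paths that reach the threshold. Mean expansion size is the sum of 5, 10, 15 or 20, each weighted by the probability of ending there, treating a pause as the end of accrual.

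| True rate p | Pause probability, given at most 1/6 | Mean expansion size |
|---|---|---|
| 20% | 7% | 19.2 |
| 25% | 16% | 18.3 |
| 30% | 29% | 17.0 |
| 33% | 38% | 16.1 |
| 40% | 60% | 13.7 |
| 50% | 85% | 10.2 |

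These figures assume that every patient's DLT status is known at each look.

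**Step 5: how far that assumption holds.** Cytopenia DLTs need at least 50 days, or 60 with reinduction, to be declared (Protocol 4.4.3). The protocol's expected accrual, 40 patients in 12 to 18 months, is 2.2 to 3.3 per month. Over 50 to 60 days (about 1.6 to 2.0 months) that is about 4 to 7 patients, roughly one block of five with an open DLT window at each look.

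**The case against.** A reader might infer that nothing checks expansion DLTs, that the expansion could never contradict the dose, or that all 20 places would be filled whatever happened. The documents do not support these readings:

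- The Section 11.3 estimator sits in the data analyses and does not exclude expansion patients. Section 11.1 summarises data by dose level with 95% CIs for percentages. On a pooled reading, the final check detects an over-limit dose about as often as the example interim looks do: 55% against 60% at a true rate of 40%, and 85% under both at 50%.
- SAP 7.4 names de-escalation as well as escalation, and Section 8.5 requires serious and unexpected severe events to reach the Medical Monitor within 24 hours.
- The figure of 20 is a ceiling, the sponsor may stop earlier, and confirming safety is not the expansion's only purpose.

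Nor do the documents say that the MTD automatically becomes the recommended Phase 2 dose; that is a separate secondary objective.

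These points narrow the concern but do not remove it. Pooling is a possible reading, not a stated rule, and other text points away from it: Section 7.1 has the MTD and DLTs defined through dose escalation, and expansion starts only after the MTD is established. Even when pooled, Section 11.3 acts at the end and attaches no consequence. The reviews in SAP 7.4 and Section 8.5 carry no DLT threshold.

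It is also fair that the 60% and 85% are conditional on passing 6 patients. Passing and then pausing has joint probability 0.233 × 0.60 = 14% at 40%, and 0.109 × 0.85 = 9% at 50%. The further requirement of at least 2 DLTs at the next dose is not modelled.

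**Conclusion.** The concern stands as a gap and an unreconciled definition. The plan does not say whether expansion DLTs enter the under-33% estimate. Its 6-patient definition cannot be carried over to 26 patients, and no DLT check or consequence applies while the expansion accrues. An over-limit dose could therefore be given to up to 20 more patients, and 9/26 DLTs could be reported as the MTD under one section while failing another.

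The chance that a too-toxic dose shows at most 1/6 is moderate: 23% at a true rate of 40% and 11% at 50%. If it does, 8 or 10 DLTs would be expected in 20 patients. The main gain from checks during accrual is earlier action, since a pooled final analysis has similar detection. The example reduces mean expansion size from 20 to about 13.7 and 10.2 at those rates. The reduction is smaller if 50- to 60-day DLT windows are still open at the looks. The true rates are assumed, and patients are treated as independent with a common DLT probability. The plan should be amended on this point.

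**What to change.** 1. State in the protocol that DLTs are assessed in expansion patients and pooled with escalation patients at the same dose. Reconcile the count-based definition (4.1, 4.3.3) with the proportion-based one (11.3).
2. Base the final MTD statement on the pooled proportion with an exact 95% CI. Add a DLT-evaluable set and a DLT table to the SAP.
3. Pre-specify periodic checks of the pooled proportion against the protocol's own 33% limit. If the limit is met, hold enrolment for safety review. Include a rule for patients whose DLT window is still open, and report the operating characteristics. Looks after 5, 10 and 15 expansion patients (4/11, 6/16, 7/21) are one example; the schedule is the sponsor's choice.

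**Cost.** Items 1 and 2 need wording and one table. Item 3 brings unnecessary pauses: with the example looks and given at most 1/6, about 7%, 16% and 29% at true DLT rates of 20%, 25% and 30%, all below the limit. At the planned accrual, waiting for cytopenia windows to close would also slow enrolment at each look; not waiting would weaken the check.
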